3.1.3 Treatment Period

The Treatment period will begin on the day of randomization (Day 1), which is to be within 28 days after the last dose of first-line systemic anti-cancer therapy or last day of local regional therapy, if applicable, and will continue until investigator-determined progressive disease (PD) (using RECIST v1.1), unacceptable toxicity, or 1 year after the first dose, whichever occurs first.

Subjects who meet eligibility criteria will be randomly assigned in a 1:1 ratio to receive one of the following centrally randomized treatments:

- Arm A: Placebo
- Arm B: CMB305

An interactive response technology (IRT) system will use the following stratification factors at the time of randomization:

- Disease status at screening: locally advanced unresectable (LAUR) vs metastatic
- Tumor response during screening: stable disease (SD)/partial response (PR) vs complete response (CR)/no evidence of disease (NED)
- Baseline presence of anti-NY-ESO-1 antibody (yes vs no)

Subjects who are randomly allocated to the placebo arm will not be permitted to cross-over to the CMB305-containing treatment arm at any time before study closure.

Tumor imaging assessments will be performed every 8 weeks after Day 1 and radiographic evidence of disease progression will be determined by the investigator using RECIST v1.1. Subjects with a global deterioration of health status requiring discontinuation of study treatment but without objective evidence of disease progression (symptomatic deterioration) will be considered as having PD for the purpose of determining PFS. Radiographic images (e.g., computed tomography [CT] scan or magnetic resonance imaging [MRI]) will also be submitted to an IRC for storage and will be available for evaluation by a central reader, if requested by the sponsor. Details for the collection and evaluation of radiographic images are included in the Radiology Manual provided to the study sites.

Tumor biopsy samples for NY-ESO-1 expression will be obtained from all subjects during the Pre-screening period as described in [Section 3.1.1](#) (either archival tumor tissue or a fresh biopsy sample). All subjects will provide peripheral blood samples for anti-NY-ESO-1 antibody assay at the screening visit for stratification.

Quality of life will be assessed up to 12 months from Day 1.

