- f Obtain and review images (CT or MRI) collected at the standard-of-care time point for the first evaluation of response to first-line systemic anti-cancer therapy. The subject's response to first-line systemic anti-cancer therapy will be assessed by the investigator using RECIST v1.1 and documented in the eCRF.
- g Tumor imaging (CT or MRI) will be performed after completion of the planned 4-cycles to 8-cycles of first-line systemic anti-cancer therapy for the evaluation of response at baseline, as assessed by the investigator using RECIST v1.1. The images collected at this time point will serve as the baseline assessment for the efficacy evaluations. These images must be collected within 28 days after the date of last dose of first-line systemic anti-cancer therapy.
- h Results from the central laboratory will be used to determine eligibility and for the safety analysis. Laboratory tests performed by the central laboratory will include: chemistry with liver function tests, lactate dehydrogenase, alkaline phosphatase, albumin, hematology with complete blood count with differential, HIV, HepB, and HepC. Coagulation samples will be drawn only at Screening and shipped to the central laboratory (prothrombin time, partial thromboplastin time, and international normalized ratio) for analysis. Urinalysis will be conducted at the central laboratory. All laboratory assessments to be performed are listed in [Table 4](#).
- i The peripheral blood on all subjects must be collected Day -28 to Day -7 during Screening and will be used for plasma ELISA testing; results of the assessment will be used for stratification and randomization.
- j For circulating tumor genomics, please see lab manual.
- k For FCBP, serum pregnancy testing will be performed during Screening.
- l Vital sign measurements will include body temperature, heart rate, respiratory rate, and resting systolic and diastolic blood pressure.
- m At Screening, the physical examination should include an evaluation of organ systems, including, but not limited to, head and neck; chest and lungs; cardiac; gastrointestinal; neurologic; endocrine; and musculoskeletal and integument. Other organ systems should be evaluated as directed by medical history or current symptoms. Measurements of body weight and height will be obtained.

Table 2 Schedule of Events for the Treatment Period through Long-term Follow-up Period

	Treatment Period								Post-Treatment Period ^c	Long-term Follow-up Period ^d

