	Prime Phase							Boost Phase	Follow-up	Follow-up
Visit	3	4	5	6	7	8	9	10+		
Timeline – Week(s)	1	3	5	7	9	11	13	Every 8 weeks ^b	Every 3 months until documentation of disease progression	Every 3 months for up to 5 years or until date of death
Timeline – Day(s)	1 ^a	22	36	50	64	78	92	Up to 1 year		
Allowed Visit Window - Days	+3	±3	±3	±3	±3	±3	±3	±7	±7	±14
Procedures										
Enrollment, stratification, and treatment allocation ^c	X									
Record prior and concomitant medications	X	X	X	X	X	X	X	X	X	X
Blood for central laboratory chemistry laboratory tests ^f	X	X		X	X		X			
Blood for central laboratory hematology ^f	X	X		X	X		X			
Urinalysis ^f	X						X			
Blood for anti-NY-ESO-1 plasma ELISA ^g	X						X			
Blood for immunity assessments ^g	X						X	X		
Blood for circulating tumor genomics ^h	X						X			
Pregnancy test ⁱ	X						X			
Vital sign measurements ^j	X	X	X	X	X	X	X	X		
Physical examination ^k	X	X	X	X	X	X	X	X		
12-lead electrocardiogram							X			
Tumor imaging with response assessment by RECIST v1.1 (CT scan or MRI) ^l					X			X	X	
ECOG Performance Status	X	X	X	X	X	X	X			
QoL assessment ^m	X						X	X		
Report AEs and SAEs ⁿ	X	X	X	X	X	X	X	X	X	X

	Treatment Period								Post-Treatment Period ^c	Long-term Follow-up Period ^d
	Prime Phase							Boost Phase	Follow-up	Follow-up
Visit	3	4	5	6	7	8	9	10+		
Timeline – Week(s)	1	3	5	7	9	11	13	Every 8 weeks ^b	Every 3 months until documentation of disease progression	Every 3 months for up to 5 years or until date of death
Timeline – Day(s)	1 ^a	22	36	50	64	78	92	Up to 1 year		
Allowed Visit Window - Days	+3	±3	±3	±3	±3	±3	±3	±7	±7	±14
Study drug administration: Placebo (Arm A) LV305 (Arm B)	X	X		X		X				
Study drug administration: Placebo (Arm A) G305 (Arm B)			X		X		X	X ^o		
Blood for LV305 persistence ^p							X	X	X	X
Tumor biopsy ^q							X			
Survival status ^r									X	X

AE = adverse event; CT = computed tomography; ECOG = Eastern Cooperative Oncology Group; IHC = immunohistochemistry; MRI = magnetic resonance imaging; NY-ESO-1 = New York esophageal squamous cell carcinoma-1; QoL = quality of life; RECIST = Response Evaluation Criteria in Solid Tumors; SAE = serious adverse event

- ^a Day 1 will occur within 28 days after the last dose of first-line systemic anti-cancer therapy or the last day of local regional therapy. Day 1 procedures must occur within 72 hours of randomization.

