3.3 Study Duration and Dates

Subject participation is inclusive of the Pre-screening, Screening, Treatment, Post-treatment, and Long-term Follow-up periods.

The Pre-screening period is up to 151 days (Day -180 to Day -29) and begins from the time the subject and/or their legally authorized representative sign the Pre-screening ICF/assent form to the time the Main Study ICF/assent form is signed. The Pre-screening period can start as early as the first dose of first-line systemic anti-cancer therapy.

The duration of the Screening period is 28 days (Day -28 to Day -1) and begins on the date the subject and/or their legally authorized representative sign the Main Study ICF/assent form and ends at time of randomization. The screening window may be extended up to 56 days by the sponsor, if a patient is recovering from toxicity related to first line systemic anti-cancer therapy, or completing local regional therapy, or baseline imaging needs adjudication to determine eligibility.

The Treatment period will begin on the day of randomization (Day 1), which is to be within 28 days after the last dose of first-line systemic anti-cancer therapy or the last day of local regional therapy, if applicable, and will continue until investigator-determined radiographic PD

(using RECIST v1.1) is documented, the occurrence of unacceptable toxicity, or until 1 year after the first dose, whichever occurs first. All visits during the Treatment period will have a window of ± 3 days from the day specified.

The Post-treatment period (for subjects who discontinue study treatment for reasons other than disease progression) will begin at the end of treatment and will continue until investigator-determined PD (using RECIST v1.1) is documented. All visits during the Post-treatment period will have a window of ± 7 days from the day specified.

The Long-term Follow-up period will begin at the time investigator-determined PD (using RECIST v1.1) is documented and will continue for up to 5 years, until the date of death, or until sponsor notification of study closure. All visits during the Long-term Follow-up period will have a window of ± 14 days from the day specified.

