4.2 Inclusion Criteria

Subjects must meet all of the following criteria to be eligible for the study.

1. Have documented histologic diagnosis of synovial sarcoma (may be confirmed by the presence of t(X;18) (p11;q11) translocation or B cell lymphoma 6 corepressor [BCOR] rearrangement) and have disease that is unresectable locally-advanced or metastatic prior to the start of first-line systemic anti-cancer therapy. Unresectable is defined as having evidence of positive surgical margins after resection of primary disease or a documented surgical consultation with assessment of an inability of resection to provide clear margins.
2. Have IHC test results from tumor biopsy for NY-ESO-1 that are positive ($\geq 1\%$ expression).
3. At the time of Pre-screening, subjects must be receiving a first-line anthracycline or ifosfamide-containing systemic anti-cancer therapy regimen (single agent ifosfamide, single agent anthracycline, combination anthracycline plus ifosfamide, or combination anthracycline plus olaratumab). Subjects must have received at least 4 cycles but no more than 8 cycles of therapy (or no more than 180 days of systemic anti-cancer therapy). Subjects who have received local regional therapy (surgical resection, radiotherapy, radiofrequency ablation, or cryotherapy) are eligible if they meet the following:
 - a. Subjects whose disease converted to operable after completion of first-line chemotherapy are eligible, if local regional therapy (surgical resection, radiotherapy, radiofrequency ablation or cryotherapy) is completed within the

- 180-day period from the date of the first dose of first-line systemic anti-cancer therapy. Please note that an extension of this 180-day period may be allowed per Section 3.3 of the protocol.
- b. Subjects whose disease remains inoperable after completion of radiotherapy are eligible if radiotherapy is completed within the 180-day period from the date of the first dose of first-line systemic anti-cancer therapy and there is no evidence of progressive disease prior to initiation of radiotherapy. Please note that an extension of this 180-day period may be allowed per Section 3.3 of the protocol.
 - c. Subjects who have PD \leq 6 months after date of last dose of adjuvant/neoadjuvant systemic anti-cancer therapy or date of last day of local regional therapy are not eligible.

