4.3 Exclusion Criteria

Subjects who meet any of the following criteria are not eligible for the study.

1. Have received the last dose of first-line systemic anti-cancer therapy or date of most recent local regional therapy >28 days prior to Day 1 (unless otherwise indicated in Section 3.3).
2. Have received prior NY-ESO-1 therapy.
3. Have received first-line systemic anti-cancer therapy with an agent other than an anthracycline-containing or ifosfamide-containing regimen (single agent anthracycline, single agent ifosfamide, combination anthracycline plus ifosfamide, or combination anthracycline plus olaratumab), or ifosfamide.
4. Have received treatment with systemic immunomodulatory agents (including, but not limited to, interleukin-2) within 28 days prior to administration of the first dose of CMB305 (i.e., Day 1) or 5 half-lives of the drug, whichever occurs sooner.
5. Have significant immunosuppression from:
 - a. Concurrent, recent (≤ 21 days prior to administration of the first CMB305 dose [i.e., Day 1]), or anticipated need for chronic treatment with systemic immunosuppressive dose of corticosteroids (the use of physiologic doses of corticosteroids may be approved after consultation with the sponsor). The use of topical or inhaled corticosteroids and mineralocorticoids (e.g., fludrocortisone) is allowed.
 - b. Other immunosuppressive medications (≤ 21 days prior to administration of the first CMB305 dose [i.e., Day 1]) including, but not limited to, cyclophosphamide, azathioprine, methotrexate, thalidomide, and anti-tumor necrosis factor (anti-TNF) agents or conditions such as common variable hypogammaglobinemia.
6. Have psychiatric, other medical illness, or any other condition that, in the opinion of the investigator, prevents compliance with the study procedures or the ability to provide valid informed consent (or assent for subjects 12 to <18 years of age).
7. Have a history of uncontrolled autoimmune disease. Uncontrolled disease is defined as one requiring chronic supra-physiologic doses of systemic steroids or other forms of immunosuppression or that requires a recently increased or newly prescribed dose within 28 days of Screening.
8. Have a significant electrocardiogram (ECG) finding or cardiovascular disease, such as New York Heart Association cardiac disease (> Class II), myocardial infarction within the previous 3 months before administration of the first dose of CMB305 (i.e., Day 1), unstable arrhythmias, or unstable angina.

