13. Have had live, attenuated vaccine administered within 28 days prior to the first scheduled dosing on Day 1 or anticipate that such a live, attenuated vaccine will be required during the study.
14. Have a history of brain metastasis.
15. Have received cancer therapies, including chemotherapy, radiation, biologic or kinase inhibitors, granulocyte colony-stimulating factor (G-CSF), or granulocyte-macrophage colony stimulating factor (GM-CSF) within 3 weeks prior to the first scheduled CMB305 dosing.
16. A FCBP who is pregnant, is planning to become pregnant, or is breast feeding; or a male who is sexually active with a FCBP who is planning to become pregnant.
17. Hypersensitivity to any ingredient of either LV305 or G305.

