5.8.1 Prior Therapy

Subjects cannot have received prior treatment with the following:

- NY-ESO-1-directed immunotherapies

Subjects must have received the last dose of first-line systemic anti-cancer therapy, or the last day of treatment with local regional therapy, if applicable, no more than 28 days prior to Day 1.

The following are prohibited within 21 days prior to the first administration of CMB305 on Day 1 or 5 half-lives of the drug (whichever is sooner):

- Any investigational agent or cancer therapy
- Immunomodulatory agents (including, but not limited to, interleukin-2)

The following are prohibited within 21 days prior to the first administration of CMB305 on Day 1:

- Immunosuppressive medications, including but not limited to, cyclophosphamide, azathioprine, methotrexate, thalidomide, and anti-TNF agents
- Any systemic anti-cancer therapy or local regional therapy (surgical resection, radiotherapy, radiofrequency ablation, cryotherapy)

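### The efficacy baseline-scan deadline (Table 1 footnote g) runs only from the last systemic dose and conflicts with the rules for subjects who then have local regional therapy

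*Protocol*

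**What the plan says.** Protocol Table 1 footnote g, repeated in SAP Table 1 footnote g, makes the scan taken after the planned 4 to 8 cycles the baseline for the efficacy evaluations. It then sets the deadline: "These images must be collected within 28 days after the date of last dose of first-line systemic anti-cancer therapy". Local regional therapy is not mentioned.

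Other timing rules do mention it:

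- **Day 1.** Protocol Section 3.1.3 puts randomization within "28 days after the last dose of first-line systemic anti-cancer therapy or last day of local regional therapy, if applicable". Table 2 footnote a agrees: "Day 1 will occur within 28 days after the last dose of first-line systemic anti-cancer therapy or the last day of local regional therapy".
- **Exclusion 1 (Section 4.3).** It refers to the last systemic dose or "date of most recent local regional therapy >28 days prior to Day 1 (unless otherwise indicated in Section 3.3").
- **Criteria 3a and 3b (Section 4.2).** Local therapy after chemotherapy may be completed within the "180-day period from the date of the first dose of first-line systemic anti-cancer therapy", and this can be extended.
- **Section 5.8.1.** The list of what is prohibited in the 21 days before Day 1 includes "Any systemic anti-cancer therapy or local regional therapy (surgical resection, radiotherapy, radiofrequency ablation, cryotherapy").
- **Section 3.3.** "The screening window may be extended up to 56 days by the sponsor", among other reasons for subjects completing local regional therapy. The footnote g deadline is not changed.

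Section 6.3.1.2 places the scan in Screening, before randomization. Section 3.1.2 assesses disease status on the most recent baseline images from Screening. The SAP gives no other tumor baseline; its general definition of baseline sits in Section 8.3, Safety Analyses.

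**The concern.** Subjects who have surgery, radiotherapy or ablation after chemotherapy are an intended part of the population: they have their own flow diagram (Figure 7) and their own eligibility clauses. For them, the disease state at randomization is the one left after local therapy. Footnote g ties the efficacy baseline to an earlier event.

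The baseline feeds investigator-assessed PFS, one of two primary endpoints either of which suffices for success, and ORR. If lesions resected or ablated after the scan remain in the baseline sum of diameters, their disappearance can register as response. It can also offset growth in the remaining target lesions at the first on-study assessment. A subject could likewise be stratified on a post-local-therapy response while the efficacy baseline shows an earlier state.

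**Working it through.** The plan states no figure on this point to reproduce. The check asks whether a scan date can satisfy all the rules at once.

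**Set-up.** Count days from the last systemic dose (day 0). Let L be the day local therapy ends, s the scan day, D the day number of Day 1, and W the length of Screening.

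- Footnote g: 0 ≤ s ≤ 28.
- Screening (Sections 3.3 and 6.3.1.2): D − W ≤ s ≤ D − 1, with W = 28, or 56 if extended.
- Day 1 (Sections 3.1.3 and 5.8.1): L + 21 ≤ D ≤ L + 28.

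**Step 1: can a compliant scan follow local therapy?** This needs L < s ≤ 28. At L = 28 the only candidate is the day local therapy ends. If L > 28 there is none, whatever the Screening length.

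**Step 2: is there any compliant date?** The earliest D is the most favorable, so the condition is L + 21 − W ≤ 28, that is L ≤ W + 7.

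| Reading | W = 28 | W = 56 |
|---|---|---|
| Day 1 at least 21 days after local therapy | L ≤ 35 | L ≤ 63 |
| Day 1 at least 22 days after (L ≤ W + 6) | L ≤ 34 | L ≤ 62 |
| No 21-day rule, D ≥ L + 1 (L ≤ W + 27) | L ≤ 55 | L ≤ 83 |

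The last row matters because exclusion 15 ("Have received cancer therapies, including chemotherapy, radiation, biologic or kinase inhibitors"), with its 3-week limit, names radiation but not surgery, radiofrequency ablation or cryotherapy. For those, the 21-day rule rests on Section 5.8.1.

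**Step 3: does eligibility allow such gaps?** Cycle length is not stated, so it is assumed. With n cycles of c days, the last cycle starts c(n − 1) days after the first dose, so the largest L under the 180-day rule is 180 − c(n − 1).

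| Cycles | c = 21 | c = 28 |
|---|---|---|
| 4 | 180 − 63 = 117 | 180 − 84 = 96 |
| 6 | 180 − 105 = 75 | 180 − 140 = 40 |
| 8 | 180 − 147 = 33 | does not fit (196 > 180) |

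These are maxima before any extension; dosing over several days within a cycle shortens them. Four-cycle courses can pass every limit above. Eight 21-day cycles can pass only the 28-day one.

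**Examples (four 21-day cycles, last dose on day 63 from the first dose).**

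- Surgery on day 95 (L = 32): footnote g closes on day 91 and 28-day Screening can open no earlier than day 95 + 21 − 28 = 88. Only days 88 to 91 comply, all before surgery.
- Local therapy ends on day 150 (L = 87): footnote g covers days 63 to 91. Screening opens no earlier than day 143, or day 115 if extended. There is no overlap.

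**Step 4: how many subjects?** The documents do not allow a count. As an illustration only: Section 1.1.3 cites an observational study in which 49% of subjects had local therapy of metastatic disease. Assume that 10% to 40% of such subjects have L > 28 with residual disease: 248 × 0.49 × (0.10 to 0.40) = 12 to 49 subjects. With exponential PFS at the design medians (4 months, and 4/0.55 = 7.27 months), the event share by week 8 (56/30.4375 = 1.84 months) is 1 − exp(−ln 2 × 1.84/4) = 27.3% on placebo and 16.1% on CMB305, mean 21.7%. That gives 2.6 to 10.5 events, or 1.9% to 7.5% of 141.

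**The case against.** **The protocol as a whole points to a scan after local therapy.** Footnote g does not forbid a later scan. Section 3.1.2 uses the most recent Screening images, and Section 3.3 extends Screening for subjects completing local therapy. Section 3.2 says the strata allow for subjects who had it, CR/NED is a stratum level, and Table 8 in Appendix 1 is keyed to no evidence of disease at Day 1. This stands. A reader might infer that the plan forces a pre-local-therapy baseline on every such subject; it does not. What remains is a conflict: with L > 28, a site that rescans follows this text but breaches a mandatory deadline in both documents.

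**Exclusion 1, read literally, removes many of these subjects**, because their last systemic dose is more than 28 days before Day 1. That reading conflicts with criteria 3a and 3b and with the if-applicable wording in Sections 3.1.3, 3.3 and 5.8.1, so it does not rescue the footnote.

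**Deviations have a process.** SAP Section 8.1.2 has the clinical team define the major deviations that exclude subjects from the EE set, with quarterly review. SAP Table 3 and the EE definition apply no scan-date test, so a late scan does not by itself censor or exclude anyone. It would be wrong to call the plan wholly silent. It is, however, not specific about this case.

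**The mechanism is narrow.** Subjects assessed as NED at Day 1 are largely protected by Table 8. Under criterion 3b, disease is irradiated rather than removed. New lesions, non-target progression and deaths still count as events. All of this stands.

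**Figure 7 and the Radiology Manual cannot be seen here** and may set a different scan time. If so, that rule would itself need reconciling with footnote g.

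**Conclusion.** The conflict is real and survives every reading tried. For L > 28, no scan that complies with footnote g can follow local therapy. Beyond about 35 or 63 days (34 and 62, or 55 and 83, on the alternative readings), no date meets both footnote g and the Screening window. Eligibility permits such gaps under the assumed cycle lengths.

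The consequence is limited to possible misclassification of response and target-lesion progression, mainly in subjects with residual measurable disease after resection or ablation. It affects investigator-assessed PFS and ORR, not OS. A reader might infer a bias in favor of CMB305 or an inflated type I error. The documents do not support that: the rule is the same in both blinded arms and the error has no fixed direction.

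Nor should the illustration of about 3 to 11 events be read as an upper bound. Its 10% to 40% factor is assumed; at 100% the same formula gives 248 × 0.49 × 0.217, about 26 events. The 49% is not stated to be local therapy after first line or within 180 days, and the week-8 rate is for all subjects. Severity: minor to moderate.

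**What to change.** Reconcile footnote g in Table 1 of both documents with Protocol Sections 3.1.2, 3.1.3, 3.3, 4.3 (exclusion 1), 5.8.1 and 6.3.1.2 and with Table 2 footnote a. One rule should define the efficacy baseline for local-therapy subjects, and that baseline should reflect disease after local therapy is complete. Check Figure 7 and the Radiology Manual against the same rule.

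Such a rule is feasible. If the scan window also ran from the last day of local therapy, the anchor that Day 1 already uses, it would span days L to L + 28. With Day 1 at L + 21 to L + 28, the days after L and before Day 1 always lie within Day −28 to Day −1, so a compliant scan after local therapy would exist for every L.

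In the SAP, state how a baseline outside the rule is handled in the PFS analysis, and whether it is a major deviation for the EE set under Section 8.1.2.

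The cost is wording in two footnotes and a short addition to the SAP. A few subjects may need a repeat scan. Sample size, endpoints and tests do not change.
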